4.4 Exploratory Secondary Study Endpoints

- Hydration administration in the clinics
- Emergency Room visits
- Hospital admissions and days spent in the hospital

5.0 STATISTICAL CONSIDERATIONS

Primary Endpoint:

The primary endpoint of the study is administration of the appropriate nutrition/pharmaceutical intervention, as defined by our algorithm, within 30 days of study enrollment. A secondary and exploratory endpoint is to assess associations between appetite scores and general quality of life measures.

Statistical Analysis:

Descriptive statistics (eg: counts, percentages) will be used to report each of the following measures:

- number of potential subjects screened
- number of potential subjects who met inclusion criteria
- number of subjects consented/enrolled
- study subject demographics
- number of subjects completing baseline assessments
- number of subjects receiving nutritional intervention following the study algorithm
- number dropped out will be presented as frequency counts and percentages along with their 95% confidence intervals

Associations between appetite scores and quality of life will be examined using analysis of variance (for continuous scale variables) and Cochran Mantel Haenzsel testing (for categorical variables). Changes in quality of life scores over time will be examined using covariance pattern models or linear mixed models, as appropriate.

Sample Size Justification:

This is a pilot study to examine the feasibility of implementing our nutritional intervention algorithm in the study population. We have based the sample size on precision in estimating the rate of feasibility. We hypothesize that we will be successful in implementing the algorithm in 85% of the study population. We will recruit a total of 30 participants, which would produce a 95% confidence interval around our point estimate of the feasibility rate whose width is 28% (i.e. 67% to 95%), based on the exact (Clopper-Pearson) formula.

Exploratory Secondary Endpoints:

Descriptive statistics will be utilized to characterize quality of life measures over time for study subjects and to characterize the frequency of outpatient IV fluid hydration episodes, Emergency Room visits, and hospital admissions in study subjects.

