2.0 AIMS

2.1 Aim 1

- To establish the feasibility of implementing an algorithm for nutrition interventions in our Cancer Center

2.2 Aim 2

- To assess associations between appetite scores and general quality of life measures in cancer patients.

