3.1 Inclusion Criteria

1. Patients with a diagnosis of head/neck, lung, pancreatic cancer, or metastatic disease of any solid primary malignancy
2. Planned, ongoing, or recently treated patient (within the past 30 days) with radiation therapy, chemotherapy, immunotherapy, and/or intravenous targeted biologic therapy
3. No previous use of appetite stimulants (steroid use for purposes other than appetite stimulant is allowed)
4. All patients must sign study specific informed consent prior to being included in the study
5. No contraindication to appetite stimulants

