4.2 Study Design

Appetite Assessments

This study will utilize the validated Council of Nutrition appetite questionnaire (CNAQ) (Appendix 2) to evaluate the effect of the nutrition intervention and pharmacological agents on patients'

appetite and nutritional intake. The CNAQ has been used in many studies as a validated questionnaire to assess appetite. The patient populations in these studies have ranged from community-dwelling adults and nursing home residents to patients with chronic diseases like ALS.²⁵⁻²⁶ It has also been used as a validated analysis of appetite in studies with patients with liver cancer in Taiwan and head and neck cancer.²⁷⁻²⁸

The patients will fill out this questionnaire weekly to assess change. If the patient scores >28 on the CNAQ, then the questionnaire will be administered biweekly, as will the nutrition education.

Quality of Life Assessments

All participants will also be asked to complete a quality of life survey (Functional Assessment of Cancer Therapy-General Population (FACT-GP), Appendix 3) on a weekly or biweekly basis at the same time as the nutrition assessment. If a patient is not present in the Medical Oncology or Radiation Therapy at the time either assessment is due, the assessments will be performed over the phone.

FACT-GP measures quality of life by asking about physical, function, emotional, and social wellbeing. In its creation, the questionnaire was modified to so it can be applicable to the general cancer population. It has been used to assess quality of life in many different sites of cancer.²⁹⁻³³

Nutritional Status

Nutritional status will be determined based on the answers to the appetite assessment and quality of life questionnaire, as well as the nutrition assessment provided by the Registered Dietitian. No lab values will be used to assess nutrition status during the course of this study.

Algorithm

The patient care will follow a pathway based on their responses to the CNAQ and clinical judgment of the physician and dietitian. The patients with fair-good appetite (score on CNAQ >24) will not receive any pharmacological agents and will receive nutrition intervention alone. Nutrition intervention will be in accordance with the Academy of Nutrition and Dietetics guidelines. The intervention will involve “purposefully planned action(s) designed with the intent of changing a nutrition-related behavior, risk factor, environmental condition, or aspect of health status”³⁴.

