The patients with poor-fair appetite (score on CNAQ <24) will be provided nutrition intervention by the Registered Dietitian and then put into one of three pharmacological groups. If the patient’s prognosis is extremely poor (<12 weeks expected survival, based on discussion with the patient’s treating physicians) and there is no additional disease modifying therapy planned, the patient will be prescribed 4mg dexamethasone (which is FDA approved), once daily, to be taken orally in the morning. Dexamethasone is given to patients with a limited expected lifespans because it has been found to be effective on a short-term basis. Also, the long-term usage of steroids has been found to myopathy and other various side effects.³⁵

If a patient has a history of marijuana use or has tried it in the past, then he/she will be prescribed medical marijuana based on financial availability due to previous exposure exhibiting better tolerance to the drug. If the marijuana is not feasible, he or she will be prescribed dronabinol (which is FDA approved). Dronabinol is used as a substitute as it contains synthetic delta-9-tetrahydrocannabinol (THC), a substrate of marijuana and therefore has a similar affect to medical marijuana. Since dronabinol is compounded similarly to medical marijuana, then for this patient population the tolerance to the medication is likely to be good.³⁶⁻³⁸

If the patient does not have any history of marijuana use, mirtazapine will be prescribed. Mirtazapine has been show to improve both appetite and quality of like in cancer patients.³⁹⁻⁴¹ Dosing mirtazapine was determined by guidelines published by the US Department of Veterans Affairs/Department of Defense. If the patient is under the age of 70, then she/he would be prescribed 15mg of mirtazapine (which is FDA approved), once daily, to be taken orally at bedtime. For geriatric population (if the

patient is over the age of 70), then she/he would be prescribed 7.5mg of mirtazapine, once daily to be taken orally at bedtime.

Refer to the flowchart (Appendix 4) for the sample pathway.

Study Duration

The study period will begin after the initial screening and immediately following study registration and last for three months.

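### Does the feasibility bullet in Section 5.0 drop the drug step and the 30-day window from the primary endpoint?

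*Combined protocol and SAP*

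**What the plan says.** Section 5.0 (Primary Endpoint) defines the primary endpoint as "administration of the appropriate nutrition/pharmaceutical intervention, as defined by our algorithm, within 30 days of study enrollment". The list under Statistical Analysis in the same section has one item that corresponds to it: "number of subjects receiving nutritional intervention following the study algorithm".

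The Sample Size Justification describes the target twice: "This is a pilot study to examine the feasibility of implementing our nutritional intervention algorithm in the study population", and then "We hypothesize that we will be successful in implementing the algorithm in 85% of the study population". It plans 30 participants and an exact (Clopper-Pearson) 95% interval of 67% to 95%, width 28%. Aim 1 (Section 2.1) is worded in the same spirit: "To establish the feasibility of implementing an algorithm for nutrition interventions in our Cancer Center".

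The algorithm in Section 4.2 has two arms. For higher scores: "The patients with fair-good appetite (score on CNAQ >24) will not receive any pharmacological agents and will receive nutrition intervention alone". For lower scores the text reads: "score on CNAQ <24) will be provided nutrition intervention by the Registered Dietitian and then put into one of three pharmacological groups". Section 3.1 selects on diagnosis ("Patients with a diagnosis of head/neck, lung, pancreatic cancer, or metastatic disease of any solid primary malignancy"), treatment, no earlier appetite stimulant, consent and no contraindication. It sets no appetite threshold.

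**The concern.** Section 4.2 uses nutrition intervention for the dietitian's part and keeps it apart from the drug groups. If the Section 5.0 bullet is read in that sense, a patient who saw the dietitian but never got the assigned drug would count as a success, and so would one served after day 30. Elsewhere (Aim 1 and the sample size text) similar words stand for the whole pathway, so the documents support both readings.

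A second worry remains even on the full reading. Patients who need no drug can enroll, and delivering advice alone takes fewer steps than also settling prognosis, marijuana history and affordability and then prescribing. With one pooled rate, good results in the easier group could cover poor delivery in the harder one. Feasibility near the hypothesized 85% could then be claimed although the drug step often failed.

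**Working it through.** **The plan's own figure.** Inputs from Section 5.0: n = 30, rate 0.85, exact two-sided 95% interval. With x = 0.85 × 30 = 25.5, the lower limit is the 2.5% quantile of Beta(x, n − x + 1) and the upper limit the 97.5% quantile of Beta(x + 1, n − x). This gives 67.3% to 95.3%, width 28.1%, as stated. The nearest whole counts are 25/30 = 83.3% (65.3% to 94.4%) and 26/30 = 86.7% (69.3% to 96.2%).

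**What the text settles.** Each element of the endpoint can be traced within Section 5.0:

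| Element | Endpoint definition | Reporting bullet | Sample size text |
|---|---|---|---|
| Drug included | named | through the reference to the algorithm | through the reference to the algorithm |
| 30-day limit | named | not repeated | not repeated |
| Denominator | not given | not given | study population, 30 participants |
| Interval | not given | not clearly attached | exact 95% |

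No row contains a contradiction. The bullet is shorter than the definition it reports, and the algorithm it refers to includes the drug groups.

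**Cost of the narrow reading.** Assume that all 30 receive dietitian advice, a share s needs a drug, and a fraction q of those receive it. The documents give neither s nor q; the ranges used are 30% to 70% and 50% to 85%. The narrow measure reads 30/30 = 100% (88.4% to 100%). The endpoint is (1 − s) + s × q:

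- s = 0.3, q = 0.5: 0.70 + 0.15 = 85%
- s = 0.5, q = 0.5: 0.50 + 0.25 = 75%
- s = 0.7, q = 0.5: 0.30 + 0.35 = 65%
- s = 0.7, q = 0.85: 0.30 + 0.595 = 89.5%

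The gap is therefore 10.5 to 35 points in these cases, but only if the analyst sets aside the definition a few lines above.

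**Masking under the full reading.** Drug-branch successes = overall successes − nutrition-only successes. Worst case, every nutrition-only patient succeeds:

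| Need a drug | Overall 25/30 | Overall 26/30 | Points below pooled rate |
|---|---|---|---|
| 10 | 25 − 20 = 5/10 = 50% | 6/10 = 60% | 33, 27 |
| 15 | 25 − 15 = 10/15 = 67% | 11/15 = 73% | 17, 13 |
| 20 | 25 − 10 = 15/20 = 75% | 16/20 = 80% | 8, 7 |
| 24 | 25 − 6 = 19/24 = 79% | 20/24 = 83% | 4, 3 |

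One nutrition-only failure adds one drug-branch success. With 10 needing a drug the rates become 6/10 and 7/10, and the gaps 23 and 17 points. With 24 they become 20/24 and 21/24, and the gap is about nil. Failures spread evenly give no gap.

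**What a split could show.** Exact drug-branch intervals in these cases run from 67.6% to 97.3% (21/24, width 29.7 points) to 18.7% to 81.3% (5/10, width 62.6 points). Only in the most extreme case, 5/10 against 20/20 (83.2% to 100%), do the two branch intervals fail to overlap.

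**Data.** The Section 7.4 spreadsheet holds appetite score, quality of life score, assessment date and medication at each visit, so delivery can be tabulated by appetite score and drug given. It lists no field for nutrition delivery, prognosis or marijuana history. But it also omits demographics, emergency visits and admissions, all of which Section 5.0 promises to report. It is evidently not the whole dataset.

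**The case for a change.** The best case for a change is that rewording one bullet costs almost nothing, while several counting rules are missing. Section 4.2 includes patients expected to live less than 12 weeks, so death before delivery is plausible, and no rule says how it counts. At n = 30 each patient moves the rate by 1/30 = 3.3 points. The appetite questionnaire is repeated weekly or biweekly, so a patient may cross the cut-off within 30 days. Section 4.2 also lets clinical judgment shape the pathway, and it speaks of prescribing where the endpoint speaks of administration.

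These gaps are real, but they are details of the kind settled when the tables are specified. On death or withdrawal, the endpoint asks whether the intervention was given within 30 days, and the hypothesized rate refers to the study population. A patient not served is then naturally a non-success among all enrolled. Dropouts are reported as well, so a reader can see the effect: leaving out one unserved patient moves 25/30 = 83.3% to 25/29 = 86.2%. The other questions would be just as open after the bullet was reworded to repeat the drug and the window.

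The argument for a branch split keeps some force: in the most extreme case above it would be informative. But that case needs a small drug branch with every failure in it, and the documents give no ground to expect either.

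**Conclusion.** The bullet is an abbreviated reference to an endpoint that the same section defines fully. Following Section 5.0 as a whole gives one pooled rate: nutrition plus drug where assigned, within 30 days, among 30 enrolled, with an exact interval whose planned width reproduces. The omission is one of wording, and analysts would fill it sensibly.

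The lack of a branch result is a fair trade-off in a pilot sized for a single rate. Masking reaches 13 to 33 points only if half or fewer need a drug and all failures fall on them; it is 3 to 4 points if 24 of 30 do, and nil if failures spread evenly. These figures rest on an assumed case mix. A descriptive tabulation remains open to the analysts, with intervals generally too wide to establish a difference between branches.

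This conclusion covers the Section 5.0 endpoint only. The different primary endpoint in Section 4.3, and the appetite score of exactly 24 that the two Section 4.2 rules leave unassigned, are separate points on which those texts need reconciling.

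### The exploratory appetite–quality-of-life association (Aim 2) is given to ANOVA and CMH with no visit, patient effect or strata named, although the two scores are paired repeatedly within 30 patients

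*Combined protocol and SAP*

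**What the plan says.** Section 2.2 gives the second of two aims: "To assess associations between appetite scores and general quality of life measures in cancer patients". Section 5.0 sets its status: "A secondary and exploratory endpoint is to assess associations between appetite scores and general quality of life measures".

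The method is one sentence in section 5.0: "Associations between appetite scores and quality of life will be examined using analysis of variance (for continuous scale variables) and Cochran Mantel Haenzsel testing", the latter for categorical variables. No visit, patient term or stratification factor is given there or elsewhere. The next sentence reads: "Changes in quality of life scores over time will be examined using covariance pattern models or linear mixed models, as appropriate". It covers change in quality of life over time, not the association with appetite.

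Section 4.2 sets the data structure. CNAQ is weekly, with one exception: "If the patient scores >28 on the CNAQ, then the questionnaire will be administered biweekly, as will the nutrition education". FACT-GP is completed "on a weekly or biweekly basis at the same time as the nutrition assessment". On duration: "The study period will begin after the initial screening and immediately following study registration and last for three months". Section 7.4 records both scores, the date and the medication at each visit. Section 5.0 also lists "number of subjects completing baseline assessments" among the descriptive measures, so a baseline data set is foreseen, but it is not tied to Aim 2.

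**The concern.** ANOVA in its plain form assumes independent observations, and CMH assumes independence within strata. Repeated scores from one patient are not independent. CMH is also undefined until its strata are named.

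The same sentence therefore allows several analyses: baseline only, all visits pooled, CMH stratified by visit, CMH stratified by patient, or a repeated-measures ANOVA. They differ greatly in precision and some are invalid. If the choice is left open, it will be made with the data in hand.

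The two questionnaires also overlap. Nausea and mood are asked in both (CNAQ items 7 and 8 in Appendix 2; the nausea and sadness items in Appendix 3). Some association is therefore expected, and the reported interval should have an honest width.

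**Working it through.** **The plan's own figure.** The only design calculation is the exact interval for feasibility. With n = 30 and x = 0.85 × 30 = 25.5, Clopper-Pearson limits are 67.3% to 95.3%, width 28.1%. This reproduces the stated 67% to 95%, width 28%. It does not bear on Aim 2, for which no precision is stated.

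**Number of pairs.** Three months is about 91 days. Weekly: 91/7 = 13 pairs per patient, at most 30 × 13 = 390. Every two weeks: 91/14 = 6.5, so 6 to 7 per patient. Death and dropout lower these counts.

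**Baseline only.** With n = 30 and a standardised slope r = 0.3:
- SE = √((1 − 0.3²)/28) = √(0.91/28) = 0.180
- 95% half-width = 2.048 × 0.180 = 0.37 FACT-GP SD per CNAQ SD
- r/SE = 1.66, giving about 36% power by the noncentral t distribution; simulation gave about 36–39%

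**Ignoring patient.** The intraclass correlation (ICC) is an assumption, because the documents give none. When both scores have the same ICC, the variance of a pooled slope is inflated by about D = 1 + (m − 1) × ICC². For m = 13:
- ICC 0.3: 1 + 12 × 0.09 = 2.08
- ICC 0.5: 1 + 12 × 0.25 = 4.00
- ICC 0.7: 1 + 12 × 0.49 = 6.88

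The 390 pairs then carry the information of about 390/2.08 = 188, 390/4.00 = 98 and 390/6.88 = 57 independent pairs.

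**Simulated false positives at a nominal 5%.** There were 4,000 trials per cell, 30 patients and no true association. Appetite was cut into three groups for ANOVA, and both scores into two for CMH.

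| Analysis | 13 visits, ICC 0.3 / 0.5 / 0.7 | 7 visits, ICC 0.3 / 0.5 / 0.7 |
|---|---|---|
| ANOVA, all visits, no patient term | 12.5 / 28.5 / 47.7% | 8.5 / 16.7 / 31.2% |
| CMH stratified by visit | 10.7 / 20.7 / 32.7% | 8.5 / 13.1 / 22.4% |
| ANOVA, one visit per patient | 5.3 / 5.2 / 5.1% | 5.2 / 5.1 / 4.7% |
| Within-patient regression | 5.2 / 5.4 / 4.6% | 5.0 / 5.9 / 4.8% |
| CMH stratified by patient | 4.7 / 5.4 / 4.8% | 4.6 / 5.5 / 5.0% |

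A second simulation used the questionnaire's own bands (8–16, 17–28, >28), an assumed CNAQ mean of 26 and SD of 5, and a skipped week after a score above 28. With up to 13 visits it gave 10–38% for pooled ANOVA and 8–23% for visit-stratified CMH. The two simulations together give the quoted ranges of 10–48% and 8–33%.

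**What the repeated-measures model gains.** At a slope of 0.3 both between and within patients:
- One common slope with patient-clustered standard errors: half-width 0.11–0.14, power 98–100%
- Patient-mean term alone: half-width 0.38–0.39, power 35–37%, about the same as baseline
- Within-patient term: power close to 100%

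**Treatment response.** Under section 4.2, a CNAQ score below 24 leads to a drug meant to raise appetite. Suppose there is no appetite–quality-of-life association, but treatment shifts both scores by an assumed 0.5 SD. Rejection rates were then about 5% for baseline, 9–12% for the patient-mean term and 10–21% for the within-patient term. Adding current medication as a covariate returned the within-patient term to about 5%. That check did not cover the patient-mean term.

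**The case against.** A reader might infer that the plan will treat all pairs as independent, so that the Aim 2 result will be invalid. The documents do not support that. They nowhere say that visits will be pooled; a baseline-only reading is natural and valid; and the next sentence of section 5.0 shows that the authors recognised repeated measures. The inflated error rates describe an analysis that the wording permits, not one that it states.

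A reader might also infer that a mixed model lifts power from about 36% to nearly 100%. It does so only for the within-patient slope, or for a single slope assumed equal between and within patients. The between-patient slope is about as wide as at baseline.

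Three further objections stand in part:
- Follow-up pairs mix association with treatment response, whereas baseline pairs do not. The follow-up pairs are therefore not simply information that a baseline analysis throws away. This affects the patient-mean term as well as the within-patient term.
- Patient-stratified CMH and GEE answer different questions. The first tests only within-patient association and drops patients whose category never changes: 15–56% of them at 13 visits and 32–69% at 7, with cuts at CNAQ 28 and median FACT-GP and the assumed CNAQ distribution. GEE gives the marginal association.
- The endpoint is exploratory, has no decision rule, and sits in a pilot sized for feasibility. That limits the severity but does not settle which analysis will be done.

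**Conclusion.** The point holds as underspecification, with a better method already in the plan. Section 5.0 does not define the Aim 2 analysis for data that come in up to about 13 pairs per patient. The valid simple reading, baseline only, has a half-width of about 0.37 SD and power of about 36–39% at a slope of 0.3. Multi-visit ANOVA without a patient term would give roughly 10–48% false positives, and visit-stratified CMH 8–33%, with 13 visits. Methods that account for patient keep about 5% when treatment does not move both scores.

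These sizes rest on an assumed ICC of 0.3–0.7 and assumed score distributions. The treatment figures rest on an assumed 0.5 SD shift. They show direction and range, not predictions.

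Severity is minor. Under the labelling in section 5.0 the association is exploratory, and neither the feasibility endpoint nor the sample of 30 is affected.

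**What to change.** In section 5.0, state:

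1. **Continuous scores.** Use the linear mixed or covariance pattern model already planned: FACT-GP on CNAQ and time, with a patient effect, separate patient-mean and within-patient CNAQ terms, and current medication as a covariate. Use patient-clustered or serial-correlation standard errors with a small-sample correction, and report slopes with 95% intervals.
2. **Categorical scores.** Use a GEE clustered by patient, with a small-sample correction, for the marginal association. Use patient-stratified CMH only for the within-patient question, and report how many patients it drops.
3. **Baseline.** Label any plain ANOVA, or CMH not stratified by patient, as baseline only, and report that result as the association free of treatment response.
4. **Interpretation.** Treat both follow-up terms as descriptive, because a low CNAQ score triggers treatment that may move both scores.

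The cost is a few sentences and slightly more analysis work. No new data are needed, because both scores, the date and the medication are already recorded at each visit. The downside is a wider between-patient interval than pooling would show (half-width about 0.38 against 0.11–0.13), but the pooled width is false precision.

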Diarrhea: Yes/No

Feel full quickly: Yes/No

Fatigue: Yes/No

Ostomy: Yes/No

Open wound or ulcer: Yes/No

Visible cachexia/muscle wasting: Yes/No

Trouble buying food: Yes/No

Assessment Completed (Auto-Calculation):

Referral to Nutritionist

Referral:

Appendix 2

Council on Nutrition Appetite Questionnaire

- 1) My appetite is
 1. Very poor
 2. Poor
 3. Average
 4. Good
 5. Very good

- 2) When I eat, I feel full after
 1. Eating only a few mouthfuls
 2. Eating about a third of a plate/meal
 3. Eating over half of a plate/meal
 4. Eating most of the food
 5. Hardly ever

- 3) I feel hungry
 1. Never
 2. Occasionally
 3. Some of the time
 4. Most of the time
 5. All of the time

- 4) Food tastes
 1. Very bad
 2. Bad
 3. Average
 4. Good
 5. Very good

- 5) Compared to when I was younger, food tastes
 1. Much worse
 2. Worse
 3. Just as good
 4. Better
 5. Much better

- 6) Normally, I eat
 1. Less than one regular meal a day
 2. One meal a day
 3. Two meals a day
 4. Three meals a day
 5. More than three meals a day (including snacks)

7) I feel sick or nauseated when I eat

1. Most times
2. Often
3. Sometimes
4. Rarely
5. Never

8) Most of the time my mood is

1. Very sad
2. Sad
3. Neither sad nor happy
4. Happy
5. Very happy

TOTAL SCORE: _____

Scoring Total the score by adding the numbers associated with the patient's response. A score of less than 28 is cause for concern. If the total is 8-16, the patient is at risk for anorexia and needs nutrition counseling. 17-28, the patient needs frequent reassessment. >28, the patient is not at risk at this time.

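### Section 5.0 plans ANOVA for the exploratory association between two numeric totals (CNAQ and FACT-GP), but defines no groups and names no method that uses both scores as numbers

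*Combined protocol and SAP*

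**What the plan says.** Section 2.2 gives the second of the study's two aims: "To assess associations between appetite scores and general quality of life measures in cancer patients". Section 5.0 ranks it: "A secondary and exploratory endpoint is to assess associations between appetite scores and general quality of life measures". For the analysis, Section 5.0 says these associations "will be examined using analysis of variance (for continuous scale variables) and Cochran Mantel Haenzsel testing (for categorical variables".

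Both scores are totals. For CNAQ, Appendix 2 instructs: "Total the score by adding the numbers associated with the" patient's response to each of eight items scored 1 to 5. Appendix 3 prints the FACT-GP items, each scored 0 to 4.

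Section 5.0 also names mixed and patterned-covariance models, but only for change in quality of life over time, not for its association with appetite. Section 4.2 has both questionnaires completed weekly or every two weeks. Section 5.0 does not say which visit or visits enter the association.

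The sample size does not rest on this aim: "We have based the sample size on precision in estimating the rate of feasibility", and "We will recruit a total of 30 participants".

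**The concern.** ANOVA in its usual form compares the mean of one variable across groups defined by another. With two numeric totals, someone must decide which score to group and where to cut it, and Section 5.0 does neither. The documents contain several CNAQ cuts that could be borrowed. Section 4.2 routes patients at 24 ("The patients with fair-good appetite (score on CNAQ >24"), with the other branch below 24, so a score of exactly 24 falls in neither. Appendix 2 uses 16 and 28. None of these is tied to the association analysis, so the cut could be chosen after the data are seen.

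Grouping also discards the differences between patients within a band. The usual ANOVA F test ignores the order of the bands as well. The output is a set of band means and a p-value. It is not the quantity a pilot would carry forward, which is the difference in FACT-GP per CNAQ point with its confidence interval.

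This applies even if only one visit per patient is analysed, so it is distinct from the question of how repeated visits are handled.

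**Working it through.** **The plan's own figure.** The only sample-size calculation is for feasibility ("We hypothesize that we will be successful in implementing the algorithm in 85% of the study population"). With n = 30 and x = 0.85 × 30 = 25.5, the Clopper-Pearson limits are the 2.5% quantile of Beta(x, n − x + 1) = Beta(25.5, 5.5), which is 67.3%, and the 97.5% quantile of Beta(x + 1, n − x) = Beta(26.5, 4.5), which is 95.3%. The width is 28.1 points. This matches the stated 67% to 95%. No comparable figure exists for Aim 2.

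**Inputs from the documents.**
- CNAQ: 8 items scored 1 to 5, so 8 × 1 = 8 to 8 × 5 = 40 (Appendix 2).
- FACT-GP: 6 + 5 + 4 + 6 = 21 printed items scored 0 to 4, so 0 to 21 × 4 = 84 (Appendix 3).
- n = 30 (Section 5.0).

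**Inputs not in the documents, assumed here.** Two-sided alpha of 5%; one pair of scores per patient; bivariate normal scores; true correlation r from 0.3 to 0.6; CNAQ grouped at the median, in thirds, in quarters, or 25/75.

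**Uncut scores.** The test statistic is t = r̂·√(28/(1 − r̂²)) on 28 degrees of freedom. As a check, the Fisher approximation is power ≈ Φ(atanh(r)·√27 − 1.96). At r = 0.5 this is Φ(0.549 × 5.196 − 1.96) = Φ(0.894) = 81%. At r = 0.3, 0.4 and 0.6 it gives 36%, 60% and 95%.

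**Grouped CNAQ.** One-way ANOVA of FACT-GP across the groups, by simulation (8,000 to 10,000 samples of 30 for each r):

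| r | Uncut | Median split | Thirds | Quarters | 25/75 split |
|---|---|---|---|---|---|
| 0.3 | 37% | 24% | 22% | 20% | 22% |
| 0.4 | 61% | 42% | 39% | 35% | 36% |
| 0.5 | 83% | 61% | 59% | 56% | 53% |
| 0.6 | 96% | 80% | 81% | 78% | 73% |

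A repeat simulation gave 37% against 20-25%, 62% against 35-42%, 83% against 54-62%, and 95% against 74-81%. The one-point differences are simulation error: the standard error near 55% with 8,000 runs is √(0.55 × 0.45/8,000) = 0.6 points. The ranges are not a floor, since a 20/80 split gives 49% at r = 0.5.

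**Information retained.** For a two-group split at proportion p with normal cut-point z, the large-sample efficiency is φ(z)²/(p(1 − p)). At the median this is 2/π = 0.64; at 25/75 it is 0.54. These correspond to roughly 0.64 × 30 = 19 and 0.54 × 30 = 16 patients analysed with uncut scores. More groups do not rescue the F test, because it spends extra degrees of freedom on unordered differences. At r = 0.5, thirds give 59% with the F test and 72% with a 1-df trend test.

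**CMH.** The 1-df correlation form is (n − 1)·r̂², referred to chi-squared on 1 df. It runs on uncut scores and has 81-83% power at r = 0.5, almost the same as the correlation test. Power falls to 34% at r = 0.5 only if both scores are first cut at their medians.

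**The case against.** The strongest reply is that the aim is exploratory. Section 5.0 says so, the 30 patients were chosen for the feasibility rate, and no decision depends on a p-value from this analysis. Power is then a weak yardstick. This stands, and it limits the weight of the point. It does not remove it, because the same loss of information affects estimation, and a slope with an interval is what exploratory work should report.

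Second, the plan never says that a score will be cut. That is correct: grouping is inferred from the named method. What the text supports is that the grouping is undefined and that no method using both totals as numbers is named. If CNAQ bands were intended, quality of life by band is a reasonable description, since the algorithm itself acts on a threshold.

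Third, a reader might infer that CMH shares the defect. The documents do not support this. Section 5.0 confines CMH to categorical variables, which could be single FACT-GP items or CNAQ bands, and its 1-df form does not need cut scores.

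Fourth, one pair per patient is not this study's data structure, because both scores are repeated over three months. This also stands. The power figures illustrate the cost of grouping and do not forecast the trial's power. The remedy therefore has to deal with repeated visits.

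**Conclusion.** The point holds as a matter of analysis choice and specification for a secondary, exploratory aim. Section 5.0 names ANOVA for the association of two numeric totals, leaves the grouping open, and names no method that would yield a slope.

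Under the stated assumptions the loss from grouping CNAQ is about 12-17 points of power at r = 0.3 (37 − 25 to 37 − 20), 20-27 at 0.4, 21-29 at 0.5 and 14-21 at 0.6. The direction is the same at every correlation tried. The size depends on a correlation, an alpha and a cut that the documents do not give.

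A reader might quote the fall from 83% to 54-62% as the trial's own loss of power. That is only the r = 0.5 case, with one pair per patient. Nor does the point undermine the sample size, which rests on feasibility and reproduces correctly.

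**What to change.** In Section 5.0, replace the ANOVA wording with:

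> The association between CNAQ and FACT-GP totals will be estimated by a linear mixed model of FACT-GP on CNAQ as a continuous covariate across all visits, with a patient-level random effect (or patterned covariance), reported as FACT-GP points per CNAQ point with 95% CI. The baseline correlation with 95% CI will also be reported. Linearity will be checked with a plot and a quadratic term.

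Keep FACT-GP means by CNAQ band as description only, and keep CMH for variables that are truly categorical.

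The slope pools differences between patients with changes within a patient; the baseline correlation shows the between-patient part alone. The cost is a short text change and an assumption of linearity, which the stated check covers. No new data are needed, and the sample-size basis does not change.
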